5.4.2 Odds ratio and 100*(1- α)% confidence interval

For an investigational drug group with n_1 subjects at risk, independent from the control group (e.g. placebo or comparator) with n_0 subjects at risk, of whom x_1 and x_0 experience a certain event with probability π_1 and π_0 respectively, the odds ratio is estimated as

$$\frac{p_1/(1-p_1)}{p_0/(1-p_0)}$$
 with $p_1=x_1/n_1$ and $p_0=x_0/n_0$. A conditional exact $100*(1-\alpha)\%$ confidence interval can be obtained by using the SAS procedure PROC FREQ with statement EXACT

OR. However, to be able to adjust for covariates odds ratios will primarily be obtained from PROC GENMOD.

5.4.3 Exposure adjusted incidence rate and 100*(1- α) % confidence interval

It will be assumed that for each of n subjects in a clinical trial the time t_j ($j=1, \dots, n$) to the first occurrence of a certain event is observed, or if the event was not experienced, the (censored) time to the end of the observation period. The sequence of first occurrences of an event will be modeled to follow approximately a Poisson process with constant intensity θ . The rate parameter θ will be estimated as $\lambda=D/T$, where

$$T = \sum_{j=1}^n t_j$$

and D is the number of subjects with at least one event. Conditionally on T, an exact 100*(1- α)% confidence interval for a Poisson variable with parameter θT and observed value D can be obtained based on (Garwood 1936), from which an exact 100*(1- α)% confidence interval for D/T will be derived as follows (Sahai 1993; Ulm 1990):

$$\text{Lower confidence limit } L = \frac{0.5c_{\alpha/2,2D}}{T} \text{ for } D>0, 0 \text{ otherwise,}$$

$$\text{Upper confidence limit } U = \frac{0.5c_{1-\alpha/2,2D+2}}{T}$$

where $c_{\alpha,k}$ is the α th quantile of the Chi-square distribution with k degrees of freedom.

The example below shows how this should be handled for cases where subjects switch treatment. In particular for summarizing 'Any AIN' as a group, one should take into consideration the sequence of treatments while calculating exposure time for subjects.

Table 16-3 Examples for calculating exposure time for incidence rates (IR)

1st treatment	1st exposure	2nd treatment	2nd exposure	Event days (in terms of study day)	Exposure for IR
Placebo	100 days	150 mg	200 days	50 (1st trt) 110 (10 days into 2nd trt)	Placebo: 50 days (event) 150 mg: 10 days (event) Any AIN: 10 days (event)

5.5 Score derivations and response criteria

5.5.1 Assessment of Spondyloarthritis International Society (ASAS)

The ASAS response measures consist of the following assessment domains ([Sieper et al 2009](#)):

[figure not shown]
1. Patient's global assessment of disease activity measured on a VAS scale.
2. Patient's assessment of IBP, represented by either total or nocturnal pain scores, both measured on a VAS scale.
3. Function represented by BASFI average of 10 questions regarding ability to perform specific tasks as measured by VAS scale.
4. Morning stiffness, represented by the average of the last 2 questions on the 6-question BASDAI regarding morning stiffness as measured by VAS scale.

[figure not shown]
ASAS response criteria (ASAS 20)

The ASAS Response Criteria (ASAS 20) was defined as an improvement of $\geq 20\%$ and ≥ 1 unit on a scale of 10 in at least 3 of the 4 main domains and no worsening of $\geq 20\%$ and ≥ 1 unit on a scale of 10 in the remaining domain.

ASAS response criteria (ASAS 40)

The ASAS 40 response was defined as an improvement of $\geq 40\%$ and ≥ 2 units on a scale of 10 in at least 3 of the 4 main domains and no worsening at all in the remaining domain.

5.5.3 Bath ankylosing spondylitis disease activity index (BASDAI)

The BASDAI consists of a 0 through 10 scale (0 being no problem and 10 being the worst problem, captured as a continuous VAS), which is used to answer 6 questions pertaining to the 5 major symptoms of axSpA:

[figure not shown]
1. Fatigue
2. Spinal pain
3. Joint pain/swelling
4. Areas of localized tenderness (called enthesitis, or inflammation of tendons and ligaments)
5. Morning stiffness duration
6. Morning stiffness severity

To give each symptom equal weighting, the mean (average) of the 2 scores relating to morning stiffness is taken (questions 5 and 6). The resulting 0 to 10 score is added to the scores from questions 1-4. The resulting 0 to 50 score is divided by 5 to give a final 0-10 BASDAI score. If one or more items are unanswered, the average of the non-missing items is used for the total score.

BASDAI 50 response is defined as at least a 50% improvement (decrease) in total BASDAI score, as compared to the Baseline total BASDAI score

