5.5.7 American college of Rheumatology (ACR) response

A patient will be considered as improved according the ACR 20 criteria if she/he has at least 20% improvement in the 2 following measures:

- Tender joint count (TJC)
- Swollen joint count (SJC)

and at least 3 of the following 5 measures:

- Patient's assessment of pain
- Patient's global assessment of disease activity
- Physician's global assessment of disease activity
- Health assessment questionnaire (HAQ[©]) score
- C-reactive protein (CRP) or erythrocyte sedimentation rate (note: CRP only will be assessed in this study)

If the number of joints for which data were available (e.g., T) is less than 78/76 for the tender/swollen joint assessment, the number of tender/swollen joints (e.g., t) will be scaled up proportionately (i.e., $78*t/T$ or $76*t/T$ for tender or swollen joint count).

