5.5.8 ASAS Health Index

The ASAS health index is a linear composite measure and contains 17 items (dichotomous response option: "I agree" and "I do not agree").

Each statement on the ASAS Health Index is given a score of 1 = I agree OR 0 = I do not agree. All item scores are summed up to give a total score that ranges from 0 (good functioning) to 17 (poor functioning). Items No 7 and 8 are not applicable for all patients. For those patients who ticked the response "not applicable", the sum score is analysed based on n=16 or n=15, respectively.

A total score can be analysed if no more than 20% of the data are missing. The total score is calculated as follows for respondents with one to a maximum of three missing responses:

$$\text{sumscore} = \frac{x}{17 - m} \times 17$$

x = Item summation score

m = Number of missing items

Cases with more than three missing responses cannot be allocated a total score.

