5.5.9 Spondyloarthritis Research Consortium of Canada (SPARCC) enthesitis index

SPARCC assessments will be performed for following entheses sites, where tenderness at each site is quantified on a dichotomous basis: 0=non-tender and 1=tender. The score is obtained by summing up these values and the range of score is 0-16.

Greater trochanter	R/L
Quadriceps tendon insertion into the patella	R/L
Patellar ligament insertion into the patella and tibial tuberosity	R/L
Achilles tendon insertion	R/L
Plantar fascia insertion	R/L
Medial epicondyles	R/L
Lateral epicondyles	R/L
Supraspinatus insertion	R/L

If the number of entheses sites for which data were available (e.g., T) is less than 16 for the SPARCC assessment, the number of tender entheses sites (e.g., t) will be scaled up proportionately (i.e., $16*t/T$ for SPARCC score).

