5.5.10 FACIT-Fatigue[©]

The FACIT-Fatigue[©] is a 13-item questionnaire. The following instructions are to be followed to calculate fatigue subscale score:

- Perform reversals as indicated for the recorded responses and sum individual items to obtain a score.
- Multiply the sum of the item scores by the number of items in the subscale, then divide by the number of items answered. This produces the subscale score.
- The higher the score, the better the QOL.

When there are missing data, prorating by subscale in this way is acceptable as long as more than 50% of the items were answered (i.e., 7 or more items were answered).

Subscale	Item Code	Reverse item?	Item response	Item Score
FATIGUE	HI7	4	-	= _____
SUBSCALE	HI12	4	-	= _____
	An1	4	-	= _____
	An2	4	-	= _____
Score range: 0-52	An3	4	-	= _____
	An4	4	-	= _____
	An5	0	+	= _____
	An7	0	+	= _____
	An8	4	-	= _____
	An12	4	-	= _____
	An14	4	-	= _____
	An15	4	-	= _____
	An16	4	-	= _____

Sum individual item scores: _____
Multiply by 13: _____
Divide by number of items answered: _____ = **Fatigue Subscale score**

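### The BASDAI missing-item rule, read over the six questions, doubles the weight of stiffness when one of Q1–Q4 is blank, and BASDAI, SPARCC and the joint counts have no minimum completeness

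*SAP*

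**What the plan says.** SAP Section 5.5.3 describes six questions covering five symptoms. Questions 5 and 6 both concern morning stiffness: "To give each symptom equal weighting, the mean (average) of the 2 scores relating to morning stiffness is taken". That mean is added to the scores for questions 1–4, and "The resulting 0 to 50 score is divided by 5 to give a final 0-10 BASDAI score". For incomplete forms the section adds one sentence: "If one or more items are unanswered, the average of the non-missing items is used for the total score". It does not say whether an item is one of the six questions or one of the five symptoms, and it sets no minimum.

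Two other scores in the appendix are scaled up from whatever was assessed:
- Section 5.5.9: whenever T, the number of sites with data, "is less than 16 for the SPARCC assessment, the number of tender entheses sites" is rescaled to 16 × t/T.
- Section 5.5.7: whenever the number of joints with data "is less than 78/76 for the tender/swollen joint assessment", the counts are rescaled to 78 × t/T (tender) or 76 × t/T (swollen).

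Three other instruments in the same appendix do have limits:
- HAQ-DI (Section 5.5.6) is not scored if more than two of its eight categories are missing.
- ASAS Health Index (Section 5.5.8): "Cases with more than three missing responses cannot be allocated a total score".
- FACIT-Fatigue (Section 5.5.10) may be prorated "as long as more than 50% of the items were answered", that is, 7 or more of 13.

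**The concern.** There are two separate problems.

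The first is weighting. The complete-data formula exists to stop stiffness counting twice. A plain average over the answered questions lets it count twice as soon as one of the other four is blank. The same symptoms then give a different total depending only on whether the form is complete. If five symptoms were meant, the text does not say so, and two programmers could derive different scores from the same form.

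The second is completeness. As written, a BASDAI total can rest on one answered question, a SPARCC score on one site and a joint count on one joint. Such values stand as observed scores although they carry little information.

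These scores feed BASDAI 50, the change in SPARCC index and ACR 20 at Week 12 (Table 1.2-1), and the baseline severity groups (Section 2.3.2), which Section 5.6.1 names among the baseline variables for supportive analyses.

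**Working it through.** **Inputs.** The BASDAI formula and missing-item rule come from Section 5.5.3, the SPARCC scaling from 5.5.9 and the joint-count scaling from 5.5.7. BASDAI 50 is a decrease of at least 50% from baseline (5.5.3). The item answers below are assumed for illustration.

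**The plan's own figure.** BASDAI = (Q1 + Q2 + Q3 + Q4 + (Q5 + Q6)/2)/5. All answers 0 gives 0 and all answers 10 gives (40 + 10)/5 = 10. The stated 0–10 range is reproduced.

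**Weight of stiffness.** Complete form: 1/5 = 20%. With one of Q1–Q4 blank, five questions remain and two of them are stiffness, so the six-question reading gives 2/5 = 40%. The five-symptom reading gives 1/4 = 25%, equal to each other answered symptom. If only Q5 or only Q6 is blank, stiffness is one of five answered questions and keeps 1/5, so the readings agree.

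**Effect on the score.** Answers 8, 8, 8, 8, 2, 2:
- complete: (32 + 2)/5 = 6.8
- Q1 blank, six questions: (24 + 4)/5 = 5.6
- Q1 blank, five symptoms: (24 + 2)/4 = 6.5

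**Effect on BASDAI 50.** Baseline all 7, score 7.0; Week 12 answers 4, 4, 4, 4, 2.5, 2.5:

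| Week 12 form | Score | Improvement | BASDAI 50 |
|---|---|---|---|
| Complete | (16 + 2.5)/5 = 3.7 | 1 − 3.7/7 = 47.1% | no |
| One of Q1–Q4 blank, six questions | (12 + 5)/5 = 3.4 | 1 − 3.4/7 = 51.4% | yes |
| One of Q1–Q4 blank, five symptoms | (12 + 2.5)/4 = 3.625 | 1 − 3.625/7 = 48.2% | no |

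**No minimum, BASDAI.** For 8, 8, 8, 8, 2, 2 with only Q5 and Q6 answered, both readings give 2.0 against a complete score of 6.8. Defining items as symptoms does not cure this.

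**No minimum, SPARCC and joints.** With T = 1, SPARCC can only be 0 or 16, the tender count 0 or 78 and the swollen count 0 or 76. Suppose 4 of 16 sites are truly tender and the assessed sites are a random subset. The scaled SPARCC then has mean 4.0 at every T, with SD (16/T) × √(T × 0.25 × 0.75 × (16 − T)/15):

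| T | SD |
|---|---|
| 1 | 6.9 |
| 4 | 3.1 |
| 8 | 1.8 |
| 15 | 0.5 |

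Under this assumption the scaling is unbiased. The cost is noise, which is large only when few sites were assessed.

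**The case against.** **The five-symptom reading.** The missing-item sentence follows directly after the step that merges Q5 and Q6, so averaging the available symptom scores is a defensible reading, and under it the weighting fault does not arise. That stands as a limit. But Sections 5.5.6, 5.5.8 and 5.5.10 all use item for a single question, and HAQ-DI has a different word, category, for grouped questions. The six-question reading is therefore the more natural one, and the text does not exclude it.

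**Any prorating moves a score.** True: the five-symptom average also moves 6.8 to 6.5. The objection here is to the change in weighting and the missing floor, not to prorating itself.

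Four stronger inferences are tempting, and the SAP does not support them:
- *Gross false responses.* With 10, 10, 10, 10, 0, 0 and three of Q1–Q4 blank, six questions give 10/3 = 3.3 against 8.0 complete, a 58% fall. Five symptoms give (10 + 0)/2 = 5.0, a 37.5% fall and no response. This needs both a very sparse form and one reading. The single-site SPARCC and joint cases are likewise extremes, and a joint count alone does not decide ACR 20, which needs both counts and three of five other measures.
- *Eligible patients dropped from the FAS.* Baseline 5, 5, 5, 5, 1, 1 scores 4.2 complete. With Q1 blank it scores (15 + 2)/5 = 3.4 over six questions, below the INCL03 limit of 4, but (15 + 1)/4 = 4.0 over five symptoms, which is not below it. The SAP does not say that INCL03 is evaluated from this derived score rather than from the eligibility check.
- *Incomplete forms certainly bypass imputation.* Section 5.6.1 allows imputation to be repeated for each component of a score, and does not say whether a BASDAI question is a component. If it is, blanks could be filled before the total is formed. This does not help SPARCC, which goes to MMRM (Section 2.7.3).
- *The primary result is at risk.* ASAS 20 uses only the two stiffness questions (Section 5.5.1), not the BASDAI total. The primary and key secondary tests could be touched only through the unproven INCL03 route.

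**Conclusion.** The point holds as a minor defect in the scoring appendix. Under the more natural reading of Section 5.5.3, a blank among Q1–Q4 with both stiffness questions answered doubles the weight of stiffness from 20% to 40%. In the illustrations this takes 6.8 to 5.6 and turns a 47.1% improvement into 51.4%. Independently of that reading, BASDAI, SPARCC and the joint counts lack the completeness limit that three other instruments in the same appendix have.

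The direct reach is BASDAI 50, SPARCC change and ACR 20, all tested outside the confirmatory framework (Section 2.7.2), together with the baseline severity groups. An effect on FAS membership would require INCL03 to be evaluated from the derived score; the single-blank example above also needs the six-question reading. The SAP gives no item-level missing rate, so the number of patients affected is unknown. It is likely small.

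**What to change.** - **Section 5.5.3:** state that Q5 and Q6 are first combined into one stiffness score, using the answered one if only one is present, and that the total is the mean of the available symptom scores.
- **Sections 5.5.3, 5.5.7 and 5.5.9:** add a completeness floor for BASDAI, SPARCC and the joint counts, in line with the other instruments. One option already in the SAP is the FACIT-Fatigue limit of more than 50%. That would mean at least 3 of 5 symptoms, 9 of 16 sites, 40 of 78 tender joints and 39 of 76 swollen joints. The appendix limits differ by instrument, so the exact cut-off is the sponsor's choice.
- **Below the floor:** set the score to missing, so that the planned multiple imputation (BASDAI 50, ACR 20) or MMRM (SPARCC) applies.

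The cost is about three sentences. The downside is that a few sparsely completed forms become missing.

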5.5.4 Bath ankylosing spondylitis functional index (BASFI)

The BASFI is a set of 10 questions designed to determine the degree of functional limitation in those patients with AS. A 0 through 10 scale (captured as a continuous VAS) is used to answer the questions. The mean of the 0 scales gives the BASFI score a value of between 0 and 10.

5.5.6 Health assessment questionnaire-disability index (HAQ-DI)

The Health Assessment Questionnaire (HAQ[©]) was developed by Stanford University and is one of the most widely used measures to assess the long-term influence of chronic disease on a subject's level of functional ability and activity restriction. The disability assessment component of the HAQ (Health Assessment Questionnaire – Disability Index), the HAQ-DI, assesses a subject's level of functional ability and includes questions of fine movements of the upper extremity, locomotor activities of the lower extremity, and activities that involve both upper and lower extremities. There are 20 questions in eight categories of functioning including dressing, rising, eating, walking, hygiene, reach, grip, and usual activities. The stem of each item asks over the past week "Are you able to ..." perform a particular task. Each item is scored on a 4-point scale from 0 to 3, representing normal (normal, no difficulty [0]), some difficulty [1], much difficulty [2], and unable to do [3].

Scoring for the eight functional categories and overall disability index scoring will be performed as follows:

There are eight categories; first score within each category:

- Dressing and Grooming, includes items 1 and 2
- Arising, includes items 3 and 4
- Eating, includes items 5, 6 and 7
- Walking, includes items 8 and 9
- Hygiene, includes items 10, 11, and 12
- Reach, includes items 13 and 14
- Grip, includes items 15, 16 and 17
- Activities, includes items 18, 19, and 20

The score for each category will be the single response within the category with the highest score (greatest difficulty). For example, in the "Eating" category, there are two answers (one for each item). If "Cut your food with a knife or fork" is marked as "3" and "Lift a full cup or glass to your mouth" is marked as "0", then the score for the "Eating" category would be "3" (the response indicating the greatest difficulty within the category). If a component question is left blank or the response is too ambiguous to assign a score, then the score for that category will be determined by the remaining completed question(s). However, if **any** "aids or devices" and/or "help from another person" items at the bottom of each page are checked, the category to which they apply will be adjusted upward to "2". If the basic score is **already** "2" or "3", the score remains unchanged. "Aids or devices" and "help from another person" can **only** change a category's score to "2"; they do **not** change the score to a "1" or a "3".

The score for the disability index will be the mean of the eight category scores. If more than two of the categories, or 25%, are missing, scale will not be scored. Otherwise, divide the sum

of the categories by the number of answered categories. The higher score indicates greater disability.

HAQ-DI response is defined by an improvement of at least 0.35 score points compared to baseline.

5.5.7 American college of Rheumatology (ACR) response

A patient will be considered as improved according the ACR 20 criteria if she/he has at least 20% improvement in the 2 following measures:

- Tender joint count (TJC)
- Swollen joint count (SJC)

and at least 3 of the following 5 measures:

- Patient's assessment of pain
- Patient's global assessment of disease activity
- Physician's global assessment of disease activity
- Health assessment questionnaire (HAQ[©]) score
- C-reactive protein (CRP) or erythrocyte sedimentation rate (note: CRP only will be assessed in this study)

If the number of joints for which data were available (e.g., T) is less than 78/76 for the tender/swollen joint assessment, the number of tender/swollen joints (e.g., t) will be scaled up proportionately (i.e., $78*t/T$ or $76*t/T$ for tender or swollen joint count).

5.5.8 ASAS Health Index

The ASAS health index is a linear composite measure and contains 17 items (dichotomous response option: "I agree" and "I do not agree").

Each statement on the ASAS Health Index is given a score of 1 = I agree OR 0 = I do not agree. All item scores are summed up to give a total score that ranges from 0 (good functioning) to 17 (poor functioning). Items No 7 and 8 are not applicable for all patients. For those patients who ticked the response "not applicable", the sum score is analysed based on n=16 or n=15, respectively.

A total score can be analysed if no more than 20% of the data are missing. The total score is calculated as follows for respondents with one to a maximum of three missing responses:

$$\text{sumscore} = \frac{x}{17 - m} \times 17$$

x = Item summation score

m = Number of missing items

Cases with more than three missing responses cannot be allocated a total score.

5.5.9 Spondyloarthritis Research Consortium of Canada (SPARCC) enthesitis index

SPARCC assessments will be performed for following entheses sites, where tenderness at each site is quantified on a dichotomous basis: 0=non-tender and 1=tender. The score is obtained by summing up these values and the range of score is 0-16.

Greater trochanter	R/L
Quadriceps tendon insertion into the patella	R/L
Patellar ligament insertion into the patella and tibial tuberosity	R/L
Achilles tendon insertion	R/L
Plantar fascia insertion	R/L
Medial epicondyles	R/L
Lateral epicondyles	R/L
Supraspinatus insertion	R/L

If the number of entheses sites for which data were available (e.g., T) is less than 16 for the SPARCC assessment, the number of tender entheses sites (e.g., t) will be scaled up proportionately (i.e., $16*t/T$ for SPARCC score).

5.5.10 FACIT-Fatigue[©]

The FACIT-Fatigue[©] is a 13-item questionnaire. The following instructions are to be followed to calculate fatigue subscale score:

- Perform reversals as indicated for the recorded responses and sum individual items to obtain a score.
- Multiply the sum of the item scores by the number of items in the subscale, then divide by the number of items answered. This produces the subscale score.
- The higher the score, the better the QOL.

When there are missing data, prorating by subscale in this way is acceptable as long as more than 50% of the items were answered (i.e., 7 or more items were answered).

Subscale	Item Code	Reverse item?	Item response	Item Score
FATIGUE	HI7	4	-	= _____
SUBSCALE	HI12	4	-	= _____
	An1	4	-	= _____
	An2	4	-	= _____
Score range: 0-52	An3	4	-	= _____
	An4	4	-	= _____
	An5	0	+	= _____
	An7	0	+	= _____
	An8	4	-	= _____
	An12	4	-	= _____
	An14	4	-	= _____
	An15	4	-	= _____
	An16	4	-	= _____

Sum individual item scores: _____
Multiply by 13: _____
Divide by number of items answered: _____ = **Fatigue Subscale score**

